We review here the arguments for lower and higher transfusion thresholds. First, data arguing for lower thresholds are discussed. A retrospective study in Brazil found an association between blood transfusions and neonatal mortality.⁴⁹ The authors found an increased relative risk of death of 1.49 (1.17-1.78) in infants who received at least one RBC transfusion compared with non-transfused infants. However, methodological difficulties include confounding analyses in such a data set – sick infants are more likely to be transfused. Moreover, in the largest neonatal RCT of high versus low hemoglobin threshold, the RR favored higher thresholds, but this effect was not statistically significant.¹ These methodological issues are discussed in a commentary editorial on dos Santos.⁵⁰ Frequent transfusions can result in iron overload, which was found at autopsy to correlate with number of transfusions given to preterm infants.⁵¹ Excess tissue iron acts as an oxidizing agent. This has implications for some of the major and serious complications affecting ELBW infants, namely ROP, BPD and NEC.^{52,53,54,55,56} Several recent studies report increased risk of NEC following blood transfusions.^{57,58,59,60,61,62,63} One such report found that blood from male donors was more likely to be associated with NEC.⁶⁴ Unfortunately, these are mainly retrospective observations, and all demonstrate, at best, association and not causality.

Finally, liberal transfusion policies must consider infection risks. Assessing the risk-benefit ratio of transfusion requires consideration of the unknown but real potential for transmission of infective agents that are undetected or even unknown.⁶⁵ With new standards of screening for the HIV virus, this agent is less prominent. However, other blood-borne agents previously not considered as potential vectors (including babesiosis and Creutzfeldt-Jakob disease variant viruses) have recently been implicated in transmission of infection.^{66,67} Cytomegalovirus (CMV) is still a potential concern despite efforts to mitigate its transmission in donated blood products.⁶⁸ Despite leukoreduction of donor blood or the use of CMV-negative donors, rates of CMV break-through infection continue at 1-3% of transfused subjects.⁶⁹ At current low rates of transmission, we acknowledge that our proposal is unlikely to be large enough to address these concerns directly.

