6.4 Prevention of Bias in an Unblinded Trial

All eligible infants of ≤ 1000 g birth weight and gestational age 22 0/7 through 28 6/7 weeks will be screened and logged, reducing selection bias. Randomization will be concealed, preventing allocation bias. It is impossible practically or ethically to blind either the caregivers or parents to the assigned hemoglobin threshold. Interim results will be presented to the Data Safety and Monitoring Committee (DSMC) with treatment assignments labeled only as group “A” or “B”. We will record all hemoglobin measures and transfusions given in order to assess protocol compliance. Site investigators will review compliance with clinicians at the onset of the trial and thereafter monthly as appropriate. Examiners at the 22-26 month examination will be unaware of treatment assignment, as will the radiologists interpreting the brain ultrasounds. Within NRN centers, local site interpretations were highly accurate and inter-rater reliability was excellent for the diagnosis of grade 3 or 4 IVH.¹³⁶

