6.7 Main secondary Outcomes

Secondary outcomes are measured at two time points:

- (A) During initial hospitalization: (i) Ultrasound grade 3 or 4 IVH, cystic PVL, or ventriculomegaly; (ii) Bell stage 2 or 3 NEC; (iii) Apnea mandating either caffeine or respiratory support; (iv) Age at final tracheal extubation; (v) Number of donor exposures by RBC donors or other blood product; (vi) Number of transfusions; (vii) ROP stage 3 or greater or requiring treatment; (viii) Time to regain birth weight; (ix) Time to full feedings; (x) Death before discharge; (xi) BPD at 36 weeks postmenstrual age based on need for oxygen supplementation following an oxygen reduction test; (xii) Decreased height, weight, or head circumference at 36 weeks postmenstrual age; (xiii) length of hospital stay at Level 3 care; and (xiv) Costs of hospitalization.
- (B) At 22-26 months corrected age, each of the composite outcomes individually: (i) Moderate or severe cerebral palsy; (ii) Severe vision impairment; (iii) Severe hearing impairment; (iv) BSID-III Cognitive score < 85; (v) BSID-III cognitive, language, or motor score <70; (vi) Gross Motor Function level \geq II; (vii) CBCL Internalizing, Externalizing, and Total Problems aggregate T scores of \geq 64 (clinical range) and 60-63 (borderline range) will be evaluated. (viii) Death before 22-26 month follow-up; (ix) Decreased height, weight, or head circumference at 22-26 month assessment; and (x) Cost-benefit analysis of primary outcome at 22-26 months.

Analyses of all primary and secondary outcomes will be adjusted for the design effects of stratification by center and birth weight group, and correlation between multiple births.

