 1. Is unexpected in terms of nature, severity, or frequency in relation to (a) the research risks that are described in the IRB-approved research protocol and informed consent document; Investigator’s Brochure or other study documents, and (b) the characteristics of the subject population being studied; **and**
 2. Is related or possibly related to participation in the research; **and**
 3. Places subjects or others at a greater risk of harm (including physical, psychological, economic, or social harm) than was previously know or recognized.

3a ii) Adverse Event (AE)

“Defined as any reaction, side effect, or untoward event that occurs during the course of the clinical trial associated with the intervention, whether or not the event is considered related to the treatment or clinically significant. A new illness, symptom, sign or clinically significant laboratory abnormality or worsening of a pre-existing condition or abnormality is considered an Adverse Event”.

AE will be monitored during the study to ensure timely detection of events that may affect the safety or continued participation of research subjects. In the TOP Trial this extremely high-risk and fragile population will each experience expected and unexpected adverse events. Adverse events and their relationship to study, severity, time of experience, expectation, actions taken to resolve the event and final outcome will be recorded as documented in the medical record, or if reported by the NICU team even before documentation. These event rates will be part of reporting the final results of the study, and for the DSMC safety monitoring.

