Secondary outcomes including comorbidities such as NEC, ROP, BPD, and NDI among survivors at follow up, as well as other binary outcomes, will be analyzed using robust Poisson regression, as described above. In addition to the stratification variables, models may also be adjusted for covariates known to be associated with the secondary outcomes in this population. For example, both gender and socioeconomic status have been implicated as crucial confounders for cognitive outcomes among survivors at follow up (53); thus, it may be appropriate to include them as covariates in models for such outcomes. Number of transfusions will be analyzed using Poisson regression. Other secondary outcomes, such as time to regain birth weight and time to full feeds, will be analyzed using Cox proportional hazards survival regression. Although the basic Cox model assumes proportional hazards between groups, if this assumption is found to be violated in our data, time-varying covariates can be added to the models to allow for changes in the proportion over time. Weekly measures of growth (weight, length, head circumference) will be analyzed using longitudinal models to test whether growth trajectories differ between treatment groups. All models incorporating the treatment effect will be adjusted for the stratification variables. All secondary outcomes analyses will be considered exploratory because the trial is not primarily powered to detect these associations.

6b) Interim Analysis and 6c) Stopping Rules

Interim analyses for safety will be conducted at four time points during the study, after 250, 500, 1000 and 1500 babies enrolled have reached status, as defined in the NRN (death, discharge, transfer, or 120 days of age, whichever occurs earlier). Rates of death and other prespecified adverse events (AEs), including NEC and adverse head US findings, will be compared between the two treatment groups. Analyses of AEs that were not prespecified may be added during the course of the study as deemed appropriate by the DSMC or the Steering Committee, in accordance with any new findings reported in the literature that may be of relevance to this trial.

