The statistical significance of interim safety analyses will be based on O'Brien Fleming bounds calculated with a Lan-DeMets spending function to preserve an overall Type-I error rate of 0.05 for a composite safety outcome of death or NEC or adverse head US findings, and tests that exceed the boundary will be considered as evidence of a statistically significant difference between treatment groups. In the event that a test approaches significance using these stopping rules, the DCC will report to the DSMC Chair who can then take appropriate action. To ensure that Drs. [name] and [name] remain blinded to evolving results, they will not be directly involved in these analyses. The results of the interim analyses will thus remain confidential, with only the trial statistician having access to unblinded data.

We recommend that the DSMC meet formally to review safety and other aspects of accruing data (such as enrollment, data completeness and protocol compliance) three times during the study, at roughly 25% , 50% and 75% of subject accrual). Formal DSMC reports will be prepared by the DCC for these meetings. These reports will include the following information:

- Brief summary of the trial design, including primary and secondary hypotheses and outcomes, study population, inclusion and exclusion criteria, recruitment, screening, randomization and study intervention procedures, and statistical considerations for trial design and analysis
- Interim monitoring plan
- Enrollment, including screening, consent, randomization and study exit
- Completeness of data and edit queries. Baseline study population characteristics, overall and by treatment group
- Treatment compliance
- Primary efficacy outcomes by treatment group, if at least 25% available
- Secondary efficacy outcomes by treatment group, if at least 25% available
- Safety outcomes, including death, by treatment group
- Protocol deviations and violations, overall and by treatment group.

These DSMC reports will be blinded, with treatments labeled as group A and group B. As per the NRN DSMC Charter, the DSMC may, however, request to be unblinded to perform their duties. If the DSMC recommends modification or cessation of the study protocol due to safety concerns, NIH will make the final determination.

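### No masking is stated for the staging of NEC, although NEC is a component of the safety boundary and a named secondary outcome

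*Combined protocol and SAP*

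**What the plan says.** Section 6.4 accepts that the intervention is open: "It is impossible practically or ethically to blind either the caregivers or parents to the assigned hemoglobin threshold". It then names the outcome assessors who are masked: "Examiners at the 22-26 month examination will be unaware of treatment assignment, as will the radiologists interpreting the brain ultrasounds". Section 6.6 repeats the masking for the follow-up assessment only.

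NEC appears as a secondary outcome in Section 4.2(h) and again in Section 6.7(A)(ii), where it is defined as "Bell stage 2 or 3 NEC". In Appendix A (Interim Analysis and Stopping Rules) it is one of three components of the outcome used for formal safety monitoring. O'Brien-Fleming bounds with a Lan-DeMets spending function are to preserve an "overall Type-I error rate of 0.05 for a composite safety outcome of death or NEC or adverse head US findings". The looks come "after 250, 500, 1000 and 1500 babies enrolled have reached status".

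No section says who assigns the Bell stage, and none provides masked reading or adjudication of it. On sources, Appendix A (3a ii) says that adverse events "will be recorded as documented in the medical record, or if reported by the NICU team even before documentation". Appendix A (3.b) has site staff capture events and site investigators review them.

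On prior belief, Section 2.5 states: "Several recent studies report increased risk of NEC following blood transfusions". The same paragraph cautions that such reports are mainly retrospective and show association at best.

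**The concern.** Of the three components of the safety composite, death needs no judgement and the head ultrasound is read masked. NEC is the one judgement-based component with no stated protection. The people who look after the infant know the arm and have a published reason to expect a link with transfusion. An equivocal case could therefore be staged differently in the two arms without anyone intending it.

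Two uses of the data are exposed. The NEC comparison could show an excess that is not real, or lose one that is. The safety composite could drift toward or away from its bound. The A/B labels on the monitoring committee's reports do not help, because they mask the people who read the results and not the person who assigns the stage.

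**Working it through.** **Inputs from the documents.** NEC 8.5% in the low arm and 5.0% in the high arm, with 80% power (Section 6.9). Death before discharge 21.5% and ultrasound brain injury 18.5% in the low arm (Section 6.9). Total 1,824 infants, allocated 1:1, so 912 per arm. Safety looks at 250, 500, 1,000 and 1,500 infants, overall type I error 0.05.

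**Assumptions, because the documents give no figure.** The misclassification rate; a true composite rate of 30-45%, equal in both arms; information proportional to infants with status out of 1,824, with error reserved for a final test at 1,824.

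**Step 1. Reproduce the plan's NEC power.** With d the difference, s0 = √(2p̄(1−p̄)/n) and s1 = √(p1(1−p1)/n + p2(1−p2)/n), power = Φ((d − 1.96·s0)/s1). For 8.5% v 5.0% this gives 81.1% at 829 per arm (1,658/2) and 84.7% at 912 per arm. The first agrees with the stated 80%.

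**Step 2. NEC alone, one final two-sided 0.05 test, 912 per arm, true rate 8.5% in both arms.** The high arm is over-called by a stated fraction of its own rate. The result is the chance of a nominally significant high-arm excess.

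| Relative over-call | Observed rates | Extra labels in 912 | Calculation | Chance |
|---|---|---|---|---|
| 0% | 8.5 v 8.5% | 0 | Φ(−1.96) | 2.5% |
| 10% | 8.5 v 9.35% | about 8 | Φ((0.0085 − 1.96×0.01335)/0.01335) | 9% |
| 20% | 8.5 v 10.2% | about 16 | Φ((0.017 − 1.96×0.01363)/0.01363) | 24% |
| 30% | 8.5 v 11.05% | about 23 | Φ((0.0255 − 1.96×0.01391)/0.01389) | 45% |

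Bias can also hide a difference. If the truth were the planned 8.5% v 5.0%, a 1-point over-call in the high arm (8.5% v 6.0%) would cut power from 84.7% to 53.9%.

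**Step 3. The safety boundary.** Spending 0.025 on each side with α(t) = 2{1 − Φ(2.241/√t)} at t = 250, 500, 1,000, 1,500 and 1,824 of 1,824 gives z bounds of 5.94, 4.12, 2.81, 2.24 and 2.04. With no bias, the chance of crossing against the high arm by the 1,500-infant look is 1.3%.

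A net excess d in the composite gives a drift of d/√(2p̄(1−p̄)/912). Recursive integration over the looks, for true composite rates of 30-45%, gives:

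| Net excess in composite | Crossing against the high arm by 1,500 |
|---|---|
| 0 | 1.3% |
| 1.7 points (20% over-call, no overlap) | 6.0-6.6% |
| 2.55 points (30% over-call, no overlap) | 11.0-12.4% |

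**Step 4. Overlap.** An over-call in an infant who has died or has an adverse ultrasound does not change the composite. Under independence, the share of infants with neither is (1 − 0.215)(1 − 0.185) = 0.640. The excesses shrink to 1.7 × 0.640 = 1.09 points and 2.55 × 0.640 = 1.63 points. The crossing chances become 3.7-3.9% and 5.7-6.3%. The same rates imply a composite of 1 − 0.640 × 0.915 = 41%, which is inside the assumed range.

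**The case against.** Five objections deserve an answer.

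- **Nothing says that unmasked staff stage NEC.** That is correct. It is an inference from unblinded caregivers, capture of events at the site and the absence of any masked review. Sections 7.1 and Appendix A (3.b) defer case report procedures to a Manual of Procedures that is not among the documents and could settle the matter. If it does, a cross-reference in Section 6.4 is enough.
- **The motive is weak.** Section 2.5 itself discounts the reports as association, and Section 6.2 says that all sites confirmed equipoise. This lowers the likely size of any bias but does not exclude it. The direction is open too: the power example in Section 6.9 has less NEC in the high arm.
- **The NEC-alone percentages might be read as chances of stopping the trial.** They are not. The boundary tests a composite under strict early bounds, and Steps 3 and 4 show far smaller effects. Nor does any scenario here create a difference as large as the planned 3.5 points; the largest is 2.55.
- **The plan limits the consequences.** Secondary analyses are labelled exploratory, the primary outcome rests on death or masked assessment, NEC and ultrasound findings are also compared separately at the looks, and NIH makes the final determination on any cessation. A signal driven by NEC alone would be visible. This stands, and it is the main reason that the point is minor.
- **Masked reading is incomplete.** It does not remove arm-dependent ordering of films. This also stands.

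**Conclusion.** The gap is real and minor. Section 6.4 masks one image-based component of the safety composite and is silent on NEC, which depends on judgement. Under assumed over-calls of 10-30%, the NEC comparison is sensitive (about 9% to 45% false high-arm excess, against 2.5%). For over-calls of 20-30%, the boundary is only modestly affected: about 4-6% after overlap, and at most about 12% without it, against 1.3%. These figures rest on assumed misclassification rates, an assumed composite rate and, for overlap, independence of the components.

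A reader might infer that NEC is known to be staged by staff aware of the arm, that the bias must run against the high arm, or that the trial stands a large chance of a false stop. The documents support none of these. Nor does the point extend to the safety boundary through retinopathy grading, because retinopathy is not in that composite.

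**What to change.** 1. Extend the masking sentence in Section 6.4 so that the radiologists whose existing reports support NEC staging are not told the study arm.
2. In Section 6.10 and Appendix A, state that for the safety boundary and the NEC analysis, stage 2-3 NEC counts when supported by that report or by surgical or pathology findings.
3. Record the bedside team's staging as well. Report two sensitivity analyses of the composite: one with bedside staging and one without NEC.
4. If the Manual of Procedures already provides masked staging, cite it in Section 6.4 instead.

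The cost is a few sentences and one case report form item, with existing local readers. The downsides are a few cases without a readable film, which would rest on surgical or pathology findings alone, and differential ordering of films, which this does not remove. The sample size is unchanged, and no change to clinical communication or care is proposed.

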6.5 Maintaining Adherence to Algorithm and Minimizing Deviation from Protocol

As noted above the algorithm will drive the majority of the transfusions. In exceptional circumstances, as defined below, the algorithm may be set aside until the infant is deemed stable to allow resumption of transfusion by study algorithm. Examples of such situations are infants with shock, severe sepsis with coagulopathy; or need for perioperative transfusion,

where the critical clinical indication for transfusion will override the threshold. In the PINT multicenter trial, the rate of deviation from protocol was acceptably low (15.9% in the low threshold arm and 6.7% in the high threshold arm). We assess adherence and separation of arms by recording mean Hgb at transfusion and at discharge. No Hgb determinations are mandated by study, but only as clinically ordered.

6.6 Choice of Primary Outcome

We will use a composite outcome of death or significant neurodevelopmental impairment in survivors at 22-26 months of corrected age. Children will be assessed at 22-26 months of corrected age by staff unaware of assignment. Centers will schedule visits as early as possible within this window. Outcome assessments will be conducted by physicians or nurses specializing in neonatal follow-up examination and certified psychologists. Neurodevelopmental Impairment will be defined in this study, as one or more of the following: cognitive delay, moderate or severe cerebral palsy, or severe visual or hearing impairment, as defined below.

Cognitive delay will be assessed by certified psychologists will assess infants using the Bayley Scales of Infant Development III (BSID-III). Cognitive delay is defined as BSID-III cognitive score < 85 (>1 standard deviation below the mean).

Cerebral Palsy is diagnosed if the child has a non-progressive motor impairment characterized by abnormal muscle tone and impaired range or control of movements. Medical history, physical examination and neurological examinations will be used to determine the presence of moderate or severe cerebral palsy (CP). Moderate CP is defined as level II or III on the Gross Motor Function Classification Scale (GMFCS).^{125,126} Severe or non-ambulatory CP consists of GMFCS IV or V.

Severe vision impairment; is defined as corrected visual acuity in the better eye less than 20/200 determined by pediatric ophthalmologists.

Severe hearing impairment, is defined as bilateral hearing loss requiring amplification or the insertion of a cochlear implant as determined by a sound field hearing assessment or auditory brainstem responses.

The primary outcome will be deemed present if one or more of the individual components of the composite outcome are known to be present, or absent if no component was present. If no component was present, one or more missing components will cause the primary outcome to be deemed missing.

Cognitive delay is defined using the cutoff of 85 in Cognitive score because the Bayley III cognitive score below 70 identifies a smaller group than the Bayley II MDI below 70. This is because the Bayley III administered at 18-22 months corrected age among children born extremely preterm results in higher scores than the Bayley II.¹³⁷ One of two alternative explanations explains this difference. Either we collectively have previously underestimated cognitive development, or current testing overestimates cognitive outcomes. We believe a conservative approach to sample size will account for potential measurement error at 22-26 months. Although the more common composite primary outcome uses a cognitive score cutoff of 70 (*i.e.*, 2 SD below the mean), we have chosen a cutoff score of 85, to answer possible effects on neurodevelopment raised by PINT, and to allow a conservative approach regarding the sample size.

At the 22-26 month follow-up, each of the composite parts of the Primary Outcome will be examined also as a secondary outcome. All secondary outcomes at this time point are listed, but they will include: behavioral, emotional and social problems as evaluated by the Child Behavior Checklist 1.5 to 5. This is a 99 item instrument that has been widely used in follow up studies. It is being utilized by the Neonatal Research Network in the Follow Up Study for extremely low birth weight infants, as well as in the follow up components of clinical other trials.

